## 13.5 Secondary Objectives, Endpoints, Analysis Plans

Generalized linear mixed models for longitudinal data will be used to compare the study groups using the standard general model  $y = X\beta + Zu + \epsilon$ , with  $y$  the response variable (e.g. secondary endpoint variable),  $X$  and  $\beta$  the design matrix and unknown parameters for the fixed effects and  $Z$  the design matrix for the random effects and  $u$  the random effects. Treatment arm (aspirin or placebo) and time visit (baseline, 6 and 12 months) will be considered fixed effects, smoking history and age at study entry random effects. Secondary endpoints include a per-lesion analysis by nodule type. Identity and logit link functions will be used for normal and binary data respectively. All tests will be two-sided and considered significant at the 5% level.

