### 3. SUMMARY OF STUDY PLAN

We will conduct a double-blind placebo-controlled phase IIb study in which participants will be randomized to receive either Aspirin (100 mg/day) or placebo for 12 months.

A total of 128 subjects will be accrued (randomized to drug or placebo); 64 per arm in a 3.5 year time period.

Participants will be men and women, current or former smokers, with undetermined subsolid lung nodules detected at low dose screening CT scan (without contrast medium) running at the EIO and MDACC. In addition, we will include subjects undergoing CT outside the context of a screening program, providing a subsolid nodule confirmation by a CT scan. Participants will be given 100 mg Aspirin daily or placebo for 12 months.

The primary endpoint will be the shrinkage of GGO and partially solid lung nodules after one-year treatment per-subject analysis.

Secondary endpoints will be the modulation of biological markers after treatment and the correlation of these findings with modification of lung nodules diameters. In particular we will evaluate the effect of Aspirin on a signature of serum miRNA correlated to subsolid nodules. Other secondary endpoints will be the per-lesion analysis including the evaluation of lung nodule density before and after treatment and the number and size of non target lesions. Additional biomarkers will include the modulation of hs-CRP, the evaluation of urinary cotinine as marker of tobacco exposure and investigation of the potential effect of aspirin according to its concentration, the measurement of urinary prostaglandin metabolites (PGEM) and urine leukotriene E4 (LTE4) both normalized to urinary creatinine concentration. Serum concentration of thromboxane B2 (TXB2) will be determined as a measure of compliance. We will also evaluate the tolerability of Aspirin at dose of 100 mg/day.

Complete physical exam and safety lab tests will be performed at 0, 6 and 12 months. Phone contact will occur at month 1, 3, 9 and 13 (i.e, one month after treatment completion).

Biomarkers: blood and urine will be collected at 0, 6 and 12 months

Lung lesions will be measured with a CT scan at 0 and 12 months. Both standard dose and low dose CT scans are allowed provided that the same procedure is used at both time points.

Duration of study will be five years: 3.5 years of accrual, one year of treatment and 0.5 year for biomarkers measurement.

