## SCHEUDLE OF EVENTS

Evaluation/ Procedure	Pre-study evaluation	Baseline Visit/Registration	Randomization	Month 1	Month 3	Month 6 visit	Month 9	Month 12 visit	Month 13	Early Termination
Informed Consent		X								
Assess pre study Eligibility (CT scan)	X									
Assess Eligibility		X								
Medical History		X								
Physical Exam/ height/weight/ vital signs		X				X		X		X
Interim medical history						X		X		X
Tobacco use assessment		X				X		X		X
Laboratory Tests		X				X		X		X
Biomarkers*§ (blood, urine)		X				X		X		
Biorepository (blood)		X						X		
CT scan					(X)¶	(X)¶		X		
Concomitant Medications	X		X	X	X	X	X	X	X	X
Baseline symptoms	X									
Dispense Study Agent			X			X				
Collect study agent						X		X		X
Compliance				X°	X°	X	X°	X		X
Review Agent Diary/Record			X			X		X		X
Adverse Events				X	X	X	X	X	X	X
Phone contact				X	X		X		X	

§Biomarkers collection at baseline, 6 and 12 month visit requires the subject to have fasted for at least 6 hours and includes TXB2 measurement; \*Blood for miRNA and urine for LTE4 and PGEM will be collected and measured at baseline and month 12 only; ° review of self reported compliance; Serum pregnancy test will be done only on potentially fertile women by β-HCG measurement; ¶ if determined to be needed during COSMOS multidisciplinary meetings

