### 8.2 Secondary Endpoints

We will investigate the effects of aspirin on the following secondary end points: (see paragraph 13.5 for a detailed statistical analysis):

*Evaluation of response according to modified RECIST criteria:*

The per-lesion analysis will be done according to the Modified RECIST criteria:

Complete Response (CR)= disappearance of the lesion

Partial Response (PR) = shrinkage of  $\geq 30\%$  of the longest diameter

Stable Disease (SD) = anything other than CR, PR or PD

Progressive Disease (PD) = growth  $\geq 20\%$ , with a minimum increase of 2 mm

The per-subject analysis will be done according to Modified RECIST criteria:

For single nodules a clinical meaningful shrinkage of 30% or more of the longest diameter will be considered as a treatment success after one year of treatment as long as there are no new non-solid or partially solid nodules or nodules highly suspicious for malignancy or shown to be malignant (modification to RECIST criteria). Growth of 20% or more with a minimum of 2 mm, will be considered progression.

For multiple lesions the sum of the maximum diameters of all target nodules will be considered, using the same parameters to define success and progression (30% or more decrease and 20% or more increase, respectively).

In case of multiple lesions, treatment will be considered successful when a complete response (CR) or partial response (PR) occurs according to modified RECIST criteria, while treatment will be considered a failure when progression of disease (PD) or stable disease (SD) occurs according to the same criteria. Specifically:

CR: disappearance of all target lesions, + no progression of non-target lesions + no appearance of new non-solid or partially solid lesions, and no appearance of new nodules highly suspicious for malignancy

or shown to be malignant (even if solid);

PR: CR for some target lesions + PR/SD for other target lesions + no PD or new lesions as described in CR above; or, PR (i.e.,  $\geq 30\%$  decrease in the sum of the longest diameter of target lesions, taking as reference the baseline sum longest diameter) for target lesions + no PD for non target lesions + no appearance of new lesions as described in CR above;

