#### *Analysis of non target lesions*

Evaluation of number and size of non target lesions before and after treatment including :

-Subsolid nodules less than 4 mm .

-Solid nodules: evaluation of number and size of preexisting or new solid nodules will be performed. The analysis will be analogous to the analysis of non-solid and partially solid nodules described above, but substituting solid lesions for subsolid lesions. In addition, a combined analysis of nonsolid and solid lesions (with solid lesions considered to be non-target lesions) will be performed.

- New nodules: A separate analysis examining new nodule appearance at 0 and 12 months

- Cancer: the rate of cancer in each arm will be assessed.

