#### *Nodule density*

We will evaluate nodule density measured by quantitative changes in mean and maximum Hounfields Unit (HU) before and after treatment.

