#### *Additional biomarkers*

Additional biomarkers will include the modulation of hs-CRP as marker of inflammation, the evaluation of urinary cotinine as marker of tobacco exposure and investigation of the potential effect of aspirin according to its concentration, the measurement of urinary PGEM and LTE4 normalized to urinary creatinine concentration. Serum TXB2 will be determined as a measure of compliance. Results will be compared between the two treatment arms (aspirin and placebo).

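### Section 13.5 lists no arm-by-visit term and no subject or lesion effect, so for biomarkers modelled as levels with baseline in the outcome the arm effect generally averages in a pre-treatment visit

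*Combined protocol and SAP*

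**What the plan says.** Section 13.5 of the combined protocol and SAP is the only model specification for the secondary endpoints. It gives a generalized linear mixed model in generic notation, lists treatment arm as a fixed effect, and continues: "time visit (baseline, 6 and 12 months) will be considered fixed effects, smoking history and age at study entry random effects". Baseline is thus a level of visit, and baseline values belong to the outcome. The same section covers lesions: "Secondary endpoints include a per-lesion analysis by nodule type". Tests are two-sided at 5%.

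The objectives ask for change. Section 1.2 asks how biomarkers change after treatment. Section 8.2 says of density: "We will evaluate nodule density measured by quantitative changes in mean and maximum Hounfields Unit (HU) before and after treatment". It also says that biomarker results will be compared between the arms.

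Most of these endpoints have two time points. The footnote to the Schedule of Events in section 7.1 says: "Blood for miRNA and urine for LTE4 and PGEM will be collected and measured at baseline and month 12 only". Section 3 says: "Lung lesions will be measured with a CT scan at 0 and 12 months". By section 10.2, hs-CRP is measured at 0, 6 and 12 months.

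**The concern.** A model with arm and visit as main effects only has one parameter that separates the arms: a single arm difference assumed to be the same at every visit. At baseline no drug effect is possible. If baseline is one of the visits in the outcome, that parameter blends a difference that is zero by design with the difference of interest. With two visits, baseline is half the data. A real aspirin effect on PGEM or LTE4 would be reported as smaller than it is, and might be missed.

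Separately, the listed random effects do not include the subject. If nothing else in the fitted model accounts for repeated measures on one person, or several nodules in one person, the standard error of the arm effect is too small.

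**Working it through.** **The plan's own figure.** Section 13.5 gives none. The only sample size calculation is in section 13.3, for the primary endpoint: effect 0.8/1.6 = 0.5 SD, n = 2(1.96 + 0.84)²/0.5², or 63 per arm by normal approximation; the exact t-test at 64 per arm has 80.1% power. It reproduces, and it bears on section 13.5 only by supplying n = 64 per arm.

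**Assumed, because the documents give no values for secondary endpoints.** Within-person correlation ρ of 0.3 to 0.7; month-12 effect of 0.3 to 0.7 SD (0.5 central); the covariance pattern; the size of the 6-month effect.

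**Step 1: what the arm coefficient estimates.** If the arm difference at visit t is δ_t, the generalized least squares arm coefficient has expectation Σ w_t δ_t, with weights proportional to V⁻¹1, where V is the within-person covariance. In expectation δ is 0 at baseline. Let D be the month-12 difference.

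- Equal variances, exchangeable correlation: each of k visits gets weight 1/k. Two visits give D/2. Three visits give 2D/3, D/2 or D/3 if the 6-month effect is full, half or nil.
- Two visits, ρ = 0.5, month-12 SD 0.8 times baseline: weights 0.286 and 0.714, so 0.71 D. With 1.25 times: 0.29 D. With 0.5 times: weights 0 and 1, so baseline drops out in that special case.
- Three visits, AR(1) at 0.5: weights 0.4, 0.2, 0.4, so 0.60, 0.50 or 0.40 D.

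**Step 2: power, with a correct exchangeable subject effect included.** Standard errors in SD units:

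- arm effect, two visits: √[(2/64)(1+ρ)/2]
- arm effect, three visits: √[(2/64)(1+2ρ)/3]
- change to month 12: √[(2/64)·2(1−ρ)]
- month-12 ANCOVA: √[(2/64)(1−ρ²)]

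At ρ = 0.5 and D = 0.5 SD: two-visit arm effect 0.25/0.153 = 1.63, power 0.372; change 0.5/0.177 = 2.83, power 0.807; ANCOVA 0.5/0.153 = 3.27, power 0.904.

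| Power at 0.5 SD | ρ = 0.3 | ρ = 0.5 | ρ = 0.7 |
|---|---|---|---|
| Arm effect, two visits | 0.419 | 0.372 | 0.335 |
| Arm effect, three visits, full 6-month effect | 0.733 | 0.637 | 0.559 |
| Arm effect, three visits, half | 0.491 | 0.410 | 0.353 |
| Arm effect, three visits, nil | 0.252 | 0.211 | 0.184 |
| Change to month 12 | 0.667 | 0.807 | 0.955 |
| Month-12 ANCOVA | 0.843 | 0.904 | 0.977 |

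At ρ = 0.5 with D = 0.3 or 0.7 SD: two-visit arm effect 17% or 63%, change 40% or 98%, ANCOVA 50% or above 99%. In one cell the arm effect beats change: three visits, full 6-month effect, ρ = 0.3 (73% against 67%). It still loses to ANCOVA (84%).

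**Step 3: type I error, only if residuals are taken as independent and no subject effect enters.** Size = 2[1 − Φ(1.96/√(1+(k−1)ρ))]. For ρ = 0.3, 0.5 and 0.7 this is 0.086, 0.110 and 0.133 with two visits, and 0.121, 0.166 and 0.206 with three. What the listed random effects do to this depends on how they enter (simulations with 64 per arm):

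- Age in whole years and smoking (current/former or whole pack-years) as grouping factors: 8% to 16% with two visits, 11% to 24% with three.
- Age unique to each subject: about 5%.
- Age as a random coefficient grouped by subject: 5.2% to 6.0% with two visits, 5.4% to 6.6% with three.

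**Step 4: lesions.** Replace 1+(k−1)ρ by the design effect 1 + ICC(E[m²]/E[m] − 1), with m nodules per person and an assumed ICC of 0.3 to 0.5. Size is 5% if everyone has one nodule, 6% to 9% if 20% to 50% have two, and 9% to 11% if all have two.

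**The case against.** **The test is not stated.** Section 13.5 lists factors; it does not say that the arm main effect is the test, and a mixed model for longitudinal data may be meant to carry a subject effect. A reader might infer that the plan commits to reporting the arm main effect as the effect of a year of aspirin. The documents do not say so, and density, worded as a change, may not be modelled as a level at all. What remains is that the arm main effect is the only between-arm parameter listed. Assuming an unstated subject effect does not repair this: the powers in step 2 already include one.

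**Scope.** A reader might infer that every secondary endpoint is affected. That is not supported.

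- Section 8.2 makes the solid-nodule analysis analogous to the subsolid one, which is referenced to baseline.
- Response is referenced to baseline too: "The per-lesion analysis will be done according to the Modified RECIST criteria". Only lesion clustering applies there.
- Outcomes with a single time point have no baseline value to mix in.
- Cotinine is an exposure marker read from a semi-quantitative strip, so SD-unit power does not apply. TXB2 serves as a compliance measure.
- Section 8.2 evaluates miRNA mainly by sensitivity, specificity and accuracy, although section 1.2 does ask for aspirin's effect on the signature.

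**Type I error.** A reader might infer that the secondary p-values will be too small. That needs independent residuals and age and smoking entered as coarse grouping factors. The documents state neither.

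**Magnitude.** Every correlation, effect and time course is assumed, and these are secondary endpoints without a power calculation. Both points stand. They limit the severity but do not remove the omission.

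**Conclusion.** The point holds for endpoints modelled as levels with baseline in the outcome: clearly hs-CRP, PGEM and LTE4, and also the miRNA signature level and nodule density if they are modelled as levels. For these, the only between-arm parameter in section 13.5 is generally not the change after treatment. The qualification is needed because some variance patterns give baseline no weight.

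Confidence in the omission is high. The size of the harm rests on the assumptions in the working. Under no true effect the baseline mixing does not bias the arm coefficient; it carries chance baseline imbalance into the estimate and dilutes a real effect. Type I inflation is a secondary, conditional matter; for per-lesion tests it also requires people with more than one nodule. The primary analysis is untouched. This should be corrected, but it does not threaten the trial's main conclusion.

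**What to change.** In section 13.5:

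- State a subject random intercept, with lesion within subject for repeated lesion measures, or an unstructured within-subject covariance.
- Make the tested contrast the arm difference at month 12. Either keep baseline in the outcome, add arm-by-visit and test the difference in change to month 12; or take baseline out of the outcome, enter it as a covariate and test the arm difference at month 12.
- For endpoints measured only at 0 and 12 months, the second route is preferable. It is then ANCOVA at month 12, with a subject random intercept where lesions are the unit.
- For per-lesion response, put a subject random intercept in the logit model.
- State how age and smoking history are coded. Whether they stay random or become fixed covariates is optional.

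The cost is SAP wording and model code. No new data are needed.

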#### Baseline and Randomization:

- Signed informed consent.

- Collection of a blood samples (safety including  $\beta$ -HCG if applicable, biomarkers including TXB2 and biorepository), urine samples (biomarkers), physical exam and medical history including baseline symptoms; concomitant medications; confirmation of eligibility criteria
- Participants are randomized to receive either study agent or placebo and will be given a 7-month supply of drug or placebo (a kit containing 7 bottles of drug or placebo, with 30 tablets in each bottle, 1 tablet per day) together with a daily calendar.

Month 1 (+/- 1 weeks from randomization):

Phone contact in order to:

- record concomitant medications and record and evaluate adverse events;
- record self-reported compliance.

Month 3 (+/- 2 weeks from randomization):

Phone contact in order to:

- record concomitant medications and record and evaluate adverse events;
- record self-reported compliance.
- confirm date of the next schedule clinic visit and blood/urine tests
- CT scan if determined to be needed during multidisciplinary meetings

Participant will be asked to return used and unused boxes at the month 6 visit.

Month 6 (+/- 2 weeks from randomization):

- Participants will undergo physical exam, vital signs, weight, lab test (including  $\beta$ -HCG, if applicable) and biological sample collection (blood, urine) for biomarker measurement including TXB2.
- Concomitant medications will be recorded and adverse events will be recorded and evaluated.
- Compliance will be measured (subjects will be asked to return both used and unused bottles as well as calendar).
- CT scan if determined to be needed during multidisciplinary meetings

A 7-month supply of drug or placebo will be provided (a kit containing 7 bottles of drug or placebo, with 30 tablets in each bottle, 1 tablet per day).

Month 9 (+/- 2 weeks from randomization):

Phone contact in order to:

- confirm date of the next CT scan and month 12 clinic visit and ;
- record concomitant medications and record and evaluate adverse events;
- record self-reported compliance.

Month 12 (+/- 2 weeks from randomization):

- Participants will undergo physical exam, vital signs, weight, lab test and biological sample collection (blood and urine) for biomarker measurement including TXB2 and biorepository.
- Concomitant medications will be recorded and toxicity will be evaluated.

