## 13.3 Accrual and Feasibility

A sample size of 128 patients (64 per arm) achieve 80% power to detect a difference of -0.8 mm between the null hypothesis that both groups average reduction is -0.2 mm and the alternative hypothesis that the average reduction of target nodules in the aspirin group is -1.0 mm, with estimated effect size of 0.5 (common standard deviations of 1.6 mm) and with a significance level (alpha) of 0.05 using a two-sided two-sample t-test. The average shrinkage in the placebo arm is derived from the Budesonide trial.

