## 13.6 Reporting and Exclusions

Patients will be considered compliant with treatment if at least 80% of the drug has been taken. Non-compliers and patients who switch the treatment assigned will be excluded from the efficacy analysis.

Patterns of observations will be classified as complete cases (no missingness), terminal (monotone) dropouts, intermittent (non-monotone) dropouts, mixed and no-data. A MCAR (Missing Completely At Random) vs. MAR (Missing At Random) statistical test will be conducted as described by Little. Kendall's  $\tau_b$  will be computed in order to test the correlation between a dichotomous indicator of missing observations and treatment assigned as well as any possible baseline covariates. Multiple imputation procedures will be adopted only for those variables whose missing data proportion will exceed the 5% value.

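### The secondary model in 13.5 has a 6-month visit level that does not fit CT, miRNA, PGEM or LTE4, and it states no arm-by-visit contrast

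*Combined protocol and SAP*

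**What the plan says.** Section 13.5 sets out one generic mixed model for secondary endpoint variables. Arm is a fixed effect, "time visit (baseline, 6 and 12 months) will be considered fixed effects", and "smoking history and age at study entry random effects". No arm-by-visit term and no participant or lesion effect is written.

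The schedule differs by endpoint:

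- **CT.** Section 3 plans lung measurement at 0 and 12 months, and 13.9 says the same in explaining why there is no interim analysis. In 7.1 the month-6 list has only a conditional entry: "CT scan if determined to be needed during multidisciplinary meetings". The same wording stands at month 3, and the table footnote ties both to COSMOS meetings.
- **CT-derived secondary endpoints.** Section 8.2 defines density and non-target number and size before and after treatment, and new nodules at 0 and 12 months.
- **miRNA, LTE4, PGEM.** The footnote to the schedule table says: "Blood for miRNA and urine for LTE4 and PGEM will be collected and measured at baseline and month 12 only".
- **hs-CRP and TXB2.** Section 10.2 collects these at baseline, 6 and 12 months. Urine is also taken at month 6 (7.3), and the footnote does not exempt cotinine.

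Section 13.6 applies multiple imputation "only for those variables whose missing data proportion will exceed the 5% value", without saying that this counts scheduled assessments only.

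**The concern.** Read literally, 13.5 creates a month-6 level for endpoints that have no planned month-6 value. For CT endpoints the only data that could fill it come from a selected subset, probably concentrated at the EIO, where the COSMOS meetings are held. No section says whether those scans enter the models, so the analyst must decide later, and under 6.9 the statistician is not blinded.

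If participants are rescanned because a nodule grew after randomisation, those scanned resemble each other across arms. Their rows then pull a pooled arm coefficient towards zero. Read literally, 13.6 could also count every month-6 CT not done as missing and call for imputing a visit that was never planned.

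At stake are the secondary nodule analyses: per-lesion size, density and non-target lesions.

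**Working it through.** **1. The plan's own figure.** Section 13.3 states: "A sample size of 128 patients (64 per arm) achieve 80% power to detect a difference of -0.8 mm", with SD 1.6 mm, "with a significance level (alpha) of 0.05 using a two-sided two-sample t-test". Normal approximation: n per arm = 2 × (1.96 + 0.84)² × (1.6/0.8)² ≈ 62.8, so 63. At 64 per arm the exact t-test power is 0.8015. The stated figure reproduces. The plan gives no figure for the secondary model.

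**2. What an arm main effect estimates.** Randomisation makes the expected baseline arm difference 0. On the plan's assumptions the month-12 difference is -1.0 - (-0.2) = -0.8 mm. With baseline and month 12 as the two levels and no interaction, the arm coefficient is the average over visits: (0 + (-0.8))/2 = -0.4 mm. This halving needs no month-6 scan.

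**3. Effect of selected month-6 scans.** Simulation with 50,000 participants per arm and three seeds.

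- From the documents: 12-month changes of -0.2 and -1.0 mm, and SD of change 1.6 mm.
- Assumed, because the documents do not say: half the effect is present at month 6, the SD of change at month 6 is 1.6/√2 = 1.13 mm, the baseline SD of the sum of diameters is 4 mm, and 10 to 40% are scanned at month 6.
- Model: arm + visit including baseline rows, fitted with and without a participant random intercept. 13.5 names no participant effect, so the fit without one is closer to the text.

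| Month-6 scans | Arm coefficient, participant intercept | Arm coefficient, none | Arm × month-12 contrast |
|---|---|---|---|
| None | -0.398 | -0.398 | -0.795 |
| Random 20% | -0.398 | -0.398 | -0.795 |
| Largest 20% at baseline | -0.398 | -0.396 | -0.795 |
| Top 10% by month-6 growth | -0.393 | -0.383 | -0.795 |
| Top 20% by month-6 growth | -0.388 | -0.368 | -0.795 |
| Top 40% by month-6 growth | -0.379 | -0.351 | -0.795 |

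Relative loss under the growth trigger:

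- With a participant intercept: 0.005/0.398 = 1.3% up to 0.019/0.398 = 4.8%.
- Without one: 0.015/0.398 = 3.8% up to 0.047/0.398 = 11.8%.

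Month-6 growth is not known when the scan is ordered, so month-3 growth is the more realistic on-study trigger. It gives less, about 1 to 4% at 10 to 30% scanned. The upper end moves by about a point with the assumptions made for month 3.

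Random scans leave the coefficient unchanged partly because the assumed month-6 difference (-0.4) equals the average of 0 and -0.8.

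**4. miRNA, PGEM, LTE4.** No month-6 value is measured, so the level has no rows. The model reduces to two visits, with no bias from this source.

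**The case against.** The strongest reply is that other sections already settle which scans count. Sections 3, 8.2 and 13.9 define the CT endpoints on baseline and month 12, no sentence sends conditional scans into a model, and 13.5 is a generic statement whose 6-month level is right for hs-CRP and TXB2. Much of this stands, and it limits the consequence. It does not remove the conflict: 13.5 names the visit levels without exception and nothing excludes the extra scans. The reminder wording in 4.4 can even be read as implying a routine month-6 CT.

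A reader might infer that month-6 scans are ordered for on-study growth, so that the arm effect is certainly biased towards zero. The documents do not say that. Section 7.1 describes the meetings as choosing a monitoring schedule, and Appendix C sets intervals by size, doubling time and progression. If the interval is fixed from the qualifying CT, selection precedes randomisation and is independent of arm. A conditional month-3 CT could supply a post-randomisation trigger, so the possibility remains, but only as a possibility.

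A reader might also fit post-baseline rows only and see the coefficient fall from -0.80 to -0.68 mm with 20% scanned on growth. That is not the model in 13.5, and most of the fall is not selection. A random 20% already gives (-0.80 + 0.2 × (-0.40))/1.2 = -0.73, because half the effect was assumed at month 6.

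On imputation, an assessment never scheduled is not ordinarily called missing. The 13.6 problem is a literal reading that one phrase would close, not a procedure the plan clearly prescribes.

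**Conclusion.** The mismatch between 13.5 and the schedule is real for the CT endpoints, miRNA, PGEM and LTE4, and should be corrected before unblinding.

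Its effect on estimates is conditional and small. The pooled arm coefficient loses about 1 to 12% if month-6 CTs are modelled and on-study growth triggered them, and essentially nothing if they are random or set from the qualifying CT. That range rests on the assumed half effect at month 6, the assumed baseline SD and 10 to 40% scanned. The empty level for miRNA, PGEM and LTE4 causes no bias.

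The primary comparison at 1 year is not affected, and the arm-by-month-12 contrast is the same under every mechanism tried. The larger issue in the same sentence is the unstated interaction: if the arm main effect is taken as the result, the effect is halved whether or not any extra scan is done.

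**What to change.** In 13.5:

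- Use baseline and month 12 only for all CT endpoints, miRNA, PGEM and LTE4. Keep the 6-month level for hs-CRP, cotinine and TXB2.
- State that unscheduled month-3 and month-6 CTs are listed and do not enter these models.
- Name the arm-by-month-12 contrast (difference between arms in change from baseline) as the treatment comparison. Dropping month 6 alone would leave the halved main effect in place.

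In 13.6, compute the missing-data proportion, classify missingness patterns and impute for scheduled assessments only.

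Reconcile the reminder wording in 4.4 and the general biomarker statement in section 3 with the schedule table.

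The cost is SAP wording. No planned data are lost and the sample size does not change.
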